3. INTRODUCTION

3.1. Study rationale

Data from clinical studies conducted in several age groups show that rMenB+OMV NZ and MenACWY are well tolerated and immunogenic when administered with a number of other vaccine antigens, including DTPa. Data from an infant study showed that both rMenB+OMV NZ and MenACWY were well tolerated and immunogenic when administered concomitantly in healthy infants (aged 3 to 13 months). No data is currently available on the concomitant use of rMenB+OMV NZ and MenACWY in adolescents.

The purpose of this clinical study is to evaluate the immunogenicity, the safety and the tolerability of rMenB+OMV NZ and MenACWY vaccines when concomitantly administered to healthy subjects 16-18 years of age.

3.2. Background

Invasive meningococcal disease (IMD) occurs when the normally asymptotically carried bacterium *Neisseria meningitidis* (*N. meningitidis*) enters the bloodstream, multiplies and causes sepsis. If the bacteria cross the blood-brain barrier, meningitis occurs [Khatami, 2010].

IMD occurs worldwide. Although incidence varies in different regions of the world, infants, children and adolescents are the most vulnerable to developing invasive disease. Symptoms of the disease occur rapidly and often result in severe outcomes within a few

hours; otherwise, healthy individuals can be permanently disabled or disfigured or die of the disease. Despite the availability of medical treatment and effective antibiotics for IMD, approximately 9% of European patients die, with case-fatality rates generally increasing with age [ECDC, 2016]. In the US, the overall case-fatality ratio remains at 10%–15%, and 11%–19% of survivors have long-term sequelae [Cohn, 2013].

No reliable estimates of the global burden of disease are currently available as case definitions differ and surveillance data from many regions are incomplete [WHO, 2011]. The overall incidence of confirmed IMDs in European countries in 2012 ranged from 0.11 to 1.77 cases per 100,000 populations [ECDC, 2016]. In the US, the incidence was 0.18 cases per 100,000 population in 2014 [Adams, 2016].

Currently, 13 serogroups of pathogenic *N. meningitidis* [Harrison, 2013] are known to exist; however, virtually all meningococcal meningitis and septicemia are caused by only six serogroups: (i.e., A, B, C, W, Y and X). The introduction of conjugate serogroup C meningococcal vaccines has dramatically changed the epidemiology of disease in industrialized nations, showing potential for broader control with A, C, W and Y conjugates, and leaving serogroup B as the predominant cause of disease. Development of vaccines for prevention of serogroup B disease in industrialized nations and serogroup A conjugate vaccines for Africa could lead to global control of meningococcal disease [Khatami, 2010].

For the US, the 2015 Centers for Disease Control (CDC) data indicate a total of 370 cases and 60 deaths attributable to meningococcal disease, with the majority of these caused by serogroup B, C and Y infections [Cohn, 2013; CDC, 2015]. In Europe, the incidence of disease due to serogroup B is particularly high in Ireland, the United Kingdom, Denmark, and Spain. These same countries had early introduction of Meningococcal serogroup C vaccination after high incidences of serogroup C infections in the late 1990s [ECDC, 2016].

In Europe, the majority of disease occurs in infants under 1 year of age, followed by children from 1 to 5 years of life. A second peak occurs in adolescents 15 to 19 years of age. In the US, incidence of meningococcal disease peaks in 3 age groups: infants and children aged <5 years, adolescents and young adults aged 16 through 21 years, and adults aged ≥65 years. Approximately 60% of disease in the first year of life is caused by serogroup B [Cohn, 2013].

Capsular polysaccharide vaccines have been used successfully in preventing disease and limiting epidemics and outbreaks caused by meningococcal serogroups A, C, W and Y.

However, the capsular polysaccharide of serogroup B is poorly immunogenic in humans, possibly due to antigenic similarities in serogroup B carbohydrate moieties to carbohydrates widely distributed in the human body. As a result, research has focused on proteins in the outer membrane of meningococci as potential antigens for candidate vaccines. Serogroup B vaccines based on protein-containing outer membrane vesicles (OMV) have been safe and effective in controlling epidemic disease caused by strains homologous to the vaccine strain in Cuba, Brazil, Chile, Norway, and New Zealand. The use of these OMV vaccines to combat serogroup B meningococcal disease has been

limited; however due to the strain-specific nature of the protection and the lack of consistent efficacy in young children.

The knowledge gained during vaccine development for the Norwegian (MenBvac) and New Zealand (MeNZB) epidemics, together with the identification of the *N. meningitidis* serogroup B genome sequence, was used to develop GSK's serogroup B meningococcal vaccine (rMenB+OMV NZ). The availability of the bacterial genome sequence allowed identification of conserved surface-exposed outer membrane proteins of serogroup B strains that were targets for bactericidal antibodies [Pizza, 2000].

CC1

A large rectangular area of the page is completely blacked out, representing redacted content. The word 'CC1' is printed in red at the top left corner of this redacted area.

On 23 January 2015, the US Food and Drug Administration approved a biologics licence application for GSK meningococcal group B vaccine according to the regulations for accelerated approval; the vaccine was approved for use in individuals 10 through 25 years of age.

Data from clinical studies conducted in several age groups show that both rMenB+OMV NZ and MenACWY are well tolerated and immunogenic when administered with a number of other vaccine antigens, including DTPa. Data from an infant study showed that both rMenB+OMV NZ and MenACWY were well tolerated and immunogenic when administered concomitantly in healthy infants [[Clinicaltrials.gov](#)]. However, no data is currently available on the concomitant use of rMenB+OMV NZ and MenACWY in adolescents.

Please refer to the current Investigator Brochure (IB) for information regarding the pre-clinical and clinical studies and the epidemiological information of *Bexsero* (rMenB+OMV NZ).

3.3. Benefit/Risk assessment

Please refer to the Prescribing Information for information regarding the summary potential risks and benefits of *Bexsero* (rMenB+OMV NZ) and *Menveo* (MenACWY).

The following section outlines the risk assessment and mitigation strategy for this study protocol:

3.3.1. Risk assessment

Important Potential/Identified Risk	Data/Rationale for Risk	Mitigation Strategy
Investigational vaccine: rMenB+OMV NZ (Bexsero)		
Important potential risk: Guillain-Barre Syndrome (GBS)	GBS has been observed with other vaccines. No cases have been identified in the Bexsero clinical development program.	The potential risk of events of possible autoimmune aetiology that might occur is mentioned in the Informed Consent Form (ICF). GBS will be monitored through the potential immune-mediated diseases (pIMDs) and SAE collection (see Section 12.5.5.2).
Important potential risk: Acute disseminated encephalomyelitis (ADEM)	ADEM has been observed with other vaccines. No cases have been reported during the Bexsero clinical development program.	The potential risk of events of possible autoimmune aetiology that can occur is mentioned in the ICF. ADEM will be monitored through the pIMD and SAE collection (see Section 12.5.5.2).
Important potential risk: Anaphylaxis and anaphylactic shock	No cases of anaphylaxis to be related to Bexsero have been reported in the Bexsero clinical development program. However, one case of anaphylaxis within 30 minutes following vaccination was reported in a third party expanded access program (V72_70TP). Allergic reaction (including anaphylactic reaction) is listed in the Bexsero US PI.	Anaphylaxis following the administration of Bexsero constitutes a contraindication (see section 7.7). Subjects will be observed closely for at least 30 minutes following the administration of the vaccines, with appropriate medical treatment readily available in case of anaphylaxis (see Section 8.2.1). Hypersensitivity, including allergy to any component of vaccines, are exclusion criteria in this study (see Section 6.2).
Important potential risk: Arthritis	This potential risk is based on a signal observed for Bexsero . Attenuated live virus vaccines (rubella) were reported to be associated with joint-related diseases [Tingle, 1986]. Among inactivated vaccines, different manifestations of arthritis following hepatitis B vaccination (psoriatic arthritis, reactive arthritis, etc.) were described [IOM, 2011]. However, no association with meningococcal vaccines has been reported in the literature. One clinical case of juvenile idiopathic arthritis (JIA) possibly related to Bexsero and 6 spontaneous reports considered to have a possible causal relationship have been observed.	Arthritis will be monitored through the AESI collection (see Section 12.5.5.1).

CONFIDENTIAL

205419 (MENB REC 2ND GEN-045 (V72_79))
Protocol Amendment 7 Final

Important Potential/Identified Risk	Data/Rationale for Risk	Mitigation Strategy
Investigational vaccine: MenACWY (Menveo)		
Important Identified risk: Reconstitution errors	Cases describing medication errors due to administration of the MenCWY conjugate liquid component only without reconstitution with the MenA conjugate lyophilized component, or due to administration of the MenA conjugate lyophilized component only after reconstitution with a different solvent, have been reported during the MenACWY clinical development program.	In several sections of the protocol (e.g., Section 7.1. "Description of study vaccines") it is clarified that the 2 vaccine components have to be reconstituted before vaccine injection.
Important potential risk: GBS	GBS has been observed with other vaccines. No cases have been reported during the MenACWY clinical development program.	The potential risk of events of possible autoimmune aetiology that might occur is mentioned in ICF. GBS will be monitored through the pIMDs and SAE collection (see Section 12.5.5.2).
Important potential risk: ADEM	ADEM has been observed with other vaccines. Two serious cases from clinical trials were retrieved from the GSK's global safety database for MenACWY. None of them has provided sufficient evidence of a causal association between ADEM and MenACWY.	The potential risk of events of possible autoimmune aetiology that can occur is mentioned in the ICF. ADEM will be monitored through the pIMD and SAE collection (see Section 12.5.5.2).
Important potential risk: Thrombocytopenia	Immune thrombocytopenic purpura has been reported in association with several licensed vaccines. One serious case related to MenACWY has been reported during the clinical development program. This case didn't provide sufficient evidence of a causal association between thrombocytopenia and MenACWY vaccine.	Immune thrombocytopenic purpura will be monitored through SAE collection (see Section 12.5.5.2).
Important potential risk: Facial paresis	Facial paresis was recognized as an important potential risk following the results of a sponsored observational study (V59_34OB) which found an imbalance of cases of facial paresis following vaccination with MenACWY, mainly when administered concomitantly with other vaccines. No cases of facial paresis were reported from interventional clinical trials.	Paralysis of the face is mentioned in the list of side effects in the ICF. Facial paresis will be monitored through SAE collection.
Study Procedures		
Risk of blood sampling	Blood sampling is associated with a risk of syncope, dizziness, and infection after or during venipuncture.	Blood samples will be obtained by a trained professional and medical assistance will be available. The potential risk of feeling faint, experiencing mild local pain, bruising, irritation or redness at the site where blood was taken, is mentioned in the ICF. The amount of blood to be taken for sampling will not be harmful to the health of the subject.

3.3.2. Benefit assessment

- Receiving GSK's meningococcal vaccines *Bexsero* and *Menveo* during the study duration may protect against meningococcal IMDs caused by *N. meningitidis* serogroups A, B, C, W, Y.
- Medical monitoring and evaluations/assessments associated with this study.

3.3.3. Overall Benefit: Risk conclusion

Taking into account the measures taken to minimize risk to subjects participating in this study, the potential or identified risks identified in association with rMenB+OMV NZ and MenACWY are justified by the potential benefits (prevention) that may be afforded to subjects receiving rMenB+OMV NZ and MenACWY.

4. OBJECTIVE(S) AND ENDPOINT(S)

Table 6 Study objectives and endpoints (Amended 11 October 2022)

Objectives	Endpoints
Primary	
To assess the safety and tolerability of rMenB+OMV NZ and MenACWY, when administered concomitantly or alone, in healthy subjects 16-18 years of age.	
 • The frequencies and percentages of subjects with solicited local (i.e., injection site pain, erythema, swelling, induration) and systemic (i.e., fever [temperature $\geq 38.0^{\circ}\text{C}/100.4^{\circ}\text{F}$], nausea, fatigue, myalgia, arthralgia, headache) adverse events (AEs) during the 7 days (including the day of vaccination) following the first (Visit 1, Day 1/Month 0), the second (Visit 3, Month 2) and the third (Visit 4, Month 3) vaccination for all groups. • The frequencies and percentages of subjects with any unsolicited AEs (including all SAEs), AEs leading to withdrawal and medically attended AEs during the 30 days (including the day of vaccination) following the first (Visit 1, Day 1/Month 0), the second (Visit 3, Month 2) and the third (Visit 4, Month 3) vaccination for all groups. • The frequencies and percentages of subjects with SAEs, AEs leading to withdrawal, and medically attended AEs, throughout the study period (Day 1/Month 0 to Month 9). • The frequencies and percentages of subjects (who received rMenB+OMV NZ) with AESI throughout the study period (Day 1/Month 0 to Month 9). • Among subjects who are followed for 12 months after their last dose: 
 ○ The frequencies and percentages of subjects with

CONFIDENTIAL

205419 (MENB REC 2ND GEN-045 (V72_79))

Protocol Amendment 7 Final

Objectives	Endpoints
	
SAEs, AEs leading to withdrawal, between SFU 5 (Month 9) and SFU 7 (Month 15).
 
The frequencies and percentages of subjects (who received rMenB+OMV NZ) with AESI between SFU 5 (Month 9) and SFU 7 (Month 15).


To demonstrate the non-inferiority of the antibody response to rMenB+OMV NZ given concomitantly with MenACWY to healthy subjects 16-18 years of age compared to rMenB+OMV NZ administered alone, as measured by serum bactericidal assay using human complement (hSBA) Geometric Mean Titers (GMTs) against N. meningitidis serogroup B indicator strains M14459 (fHbp), 96217 (NadA), NZ98/254 (PorA) and M07-0241084* (NHBA), at one month after the second vaccination with rMenB+OMV NZ.
 
Criterion: Non-inferiority will be demonstrated if for each of the four serogroup B test strains, the lower limit of the 2-sided 95% confidence interval of the between-group ratio of hSBA GMTs (rMenB+OMV NZ with MenACWY versus rMenB+OMV NZ alone) is >0.5.
	
Co-primary endpoints for Group MenB+MenACWY and Group MenB are the hSBA GMTs for rMenB+OMV NZ against each of the four serogroup B test strains (M14459, 96217, NZ98/254 and M07-0241084) at one month after the second vaccination with rMenB+OMV NZ (Visit 4, Month 3).

To demonstrate the non-inferiority of the antibody response to MenACWY given concomitantly with rMenB+OMV NZ to healthy subjects 16-18 years of age compared to MenACWY administered alone, as measured by hSBA GMTs against each of the N. meningitidis serogroups A, C, W and Y, at one month after the (study) vaccination with MenACWY.
 
Criterion: Non-inferiority will be demonstrated if for each of the four serogroups A, C, W and Y, the lower limit of the 2-sided 95% confidence interval of the between-group ratio of hSBA GMTs (rMenB+OMV NZ with MenACWY versus MenACWY alone) is >0.5.
	
Co-primary endpoints for Group MenB+MenACWY and Group MenACWY are the hSBA GMTs against each of the four serogroups A, C, W and Y with MenACWY at one month after the study vaccination of MenACWY (Visit 2, Month 1).

Secondary	

To assess the non-inferiority of the responses to MenACWY when given concomitantly with rMenB+OMV NZ to healthy subjects 16-18 years of age compared to MenACWY administered alone as measured by Enzyme-Linked Immunosorbent Assay (ELISA) Geometric Mean Concentration (GMCs) against each of the serogroups A, C, W and Y, at one month after the (study) vaccination with MenACWY.
 
Criterion: Non-inferiority will be demonstrated if for each of the four A, C, W and Y strains, the lower limit of the 2-sided 95% confidence interval of the between-group ratio of ELISA GMCs (MenACWY with rMenB+OMV NZ versus MenACWY alone) is >0.5.
	
Immune response to MenACWY
 
The immune response to MenACWY when administered with/without rMenB+OMV NZ one month after the first vaccination (Visit 2, Month 1, Groups MenB+MenACWY and MenACWY) will be assessed for the serogroups A, C, W and Y as ELISA GMCs.

To assess the immune response to rMenB+OMV NZ in healthy subjects 16-18 years of age against N. meningitidis serogroup B test strains M14459 (fHbp), 96217 (NadA), NZ98/254 (PorA) and M07-0241084 (NHBA), at one month after the first and the second vaccination with rMenB+OMV NZ.
	
Immune response to rMenB+OMV NZ
 
The immune response to rMenB+OMV NZ when administered with/without MenACWY will be evaluated by measuring bactericidal activity against N. meningitidis serogroup B test strains M14459, 96217, NZ98/254 and M07-0241084 in both MenB+MenACWY and MenB Groups as following:

CONFIDENTIAL

205419 (MENB REC 2ND GEN-045 (V72_79))

Protocol Amendment 7 Final

Objectives	Endpoints
	
 • GMTs at one month after first (Visit 2, Month 1) and second (Visit 4, Month 3) vaccination with rMenB+OMV NZ and Geometric Mean Ratio (GMRs) at one month after the first and the second rMenB+OMV NZ vaccination compared to the baseline at Visit 1, Day 1/Month 0. • The percentage of subjects with hSBA titers \geq Lower Limit of Quantitation (LLOQ) for each and all serogroup B test strains, one month after the first (Visit 2, Month 1) and second (Visit 4, Month 3) vaccination. • The percentage of subjects with fourfold increase in hSBA titers relative to baseline (Visit 1, Day 1/Month 0) defined as: 
 – For a pre-vaccination titer $<$ limit of detection (LOD), a post-vaccination titer (Visit 2, Month 1 and Visit 4, Month 3) of \geq fourfold the LOD or \geq LLOQ, whichever is greater, – For a pre-vaccination titer \geq LOD but $<$ LLOQ, a post vaccination titer (Visit 2, Month 1 and Visit 4, Month 3) of at least fourfold the LOD, – For a pre-vaccination titer \geq LLOQ, a post vaccination titer (Visit 2, Month 1 and Visit 4, Month 3) of at least fourfold the pre-vaccination titer (for Groups MenB+MenACWY and MenB). • The ratio of GMTs (rMenB+OMV NZ when administered with MenACWY [Group MenB+MenACWY] versus rMenB+OMV NZ when administered alone [Group MenB]), one month after the first vaccination (Visit 2, Month 1).
To assess the immune response to MenACWY in healthy subjects 16-18 years of age against each of the serogroups A, C, W and Y, at one month after the (study) vaccination with MenACWY.	
Immune response to MenACWY
 
The immune response to MenACWY when administered with/without rMenB+OMV NZ at baseline (i.e. pre-vaccination, Visit 1, Day 1/Month 0) and at one month after the first vaccination (Visit 2, Month 1; Groups MenB+MenACWY and MenACWY) will be assessed for the serogroups A, C, W and Y as:
 
 • The percentage of subjects with hSBA titers \geq LLOQ, for each serogroup. • GMRs at one month after first vaccination compared to baseline • The percentage of subjects with fourfold increase in hSBA titers relative to baseline (Visit 1, Day 1/Month 0) is defined as: 
 – For a pre-vaccination titer $<$ LOD, a post-vaccination titer (Visit 2, Month 1) of \geq fourfold the LOD or \geq LLOQ, whichever is greater,

Objectives	Endpoints
CCI	
 – For a pre-vaccination titer \geq LOD but $<$ LLOQ, a post vaccination titer (Visit 2, Month 1) of at least fourfold the LLOQ, – For a pre-vaccination titer \geq LLOQ, a post vaccination titer (Visit 2, Month 1) of at least fourfold the pre-vaccination titer (for Groups MenB+MenACWY and MenACWY).

*The NHBA indicator strain M07-0241084 may be subject to change during the study, before clinical testing starts. In this case, this change will be documented in the clinical report.

The study will be deemed successful if both:

1. the non-inferiority of the antibody response to rMenB+OMV NZ when given concomitantly with MenACWY versus rMenB+OMV NZ alone and
2. the non-inferiority of the antibody response to MenACWY when given concomitantly with rMenB+OMV NZ versus MenACWY alone are demonstrated.

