
To assess the immune response to rMenB+OMV NZ in healthy subjects 16-18 years of age against N. meningitidis serogroup B test strains M14459 (fHbp), 96217 (NadA), NZ98/254 (PorA) and M07-0241084* (NHBA), at one month after the first and the second vaccination with rMenB+OMV NZ.
	
Immune response to rMenB+OMV NZ The immune response to rMenB+OMV NZ when administered with/without MenACWY will be evaluated by measuring bactericidal activity against N. meningitidis serogroup B test strains M14459, 96217, NZ98/254 and M07-0241084 in both MenB+MenACWY and MenB Groups as following:
 
 GMTs at one month after first and second vaccination with rMenB+OMV NZ and Geometric Mean Ratio (GMRs) at one month after the first (Visit 2, Month 1) and the second (Visit 4, Month 3) rMenB+OMV NZ vaccination compared to the baseline at Visit 1, Day 1/Month 0. The percentage of subjects with hSBA titers \geq Lower Limit of Quantitation (LLOQ) for each and all serogroup B test strains, one month after the first (Visit 2, Month 1) and second (Visit 4, Month 3) vaccination. The percentage of subjects with fourfold increase in hSBA titers relative to baseline (Visit 1, Day 1/Month 0) is defined as: 
 For a pre-vaccination titer $<$ limit of detection (LOD), a post-vaccination titer (Visit 2, Month 1 and Visit 4, Month 3) of \geq fourfold the LOD or \geq LLOQ, whichever is greater, For a pre-vaccination titer \geq LOD but $<$ LLOQ, a post vaccination titer (Visit 2, Month 1 and Visit 4, Month 3) of at least fourfold the LLOQ,

CONFIDENTIAL

205419 (MENB REC 2ND GEN-045 (V72_79))

Protocol Amendment 7 Final

Objectives	Endpoints
	
 – For a pre-vaccination titer \geq LLOQ, a post vaccination titer (Visit 2, Month 1 and Visit 4, Month 3) of at least fourfold the pre-vaccination titer (for Groups MenB+MenACWY and MenB). • The ratio of GMTs (rMenB+OMV NZ when administered with MenACWY [Group MenB+MenACWY] versus rMenB+OMV NZ when administered alone [Group MenB]), one month after the first vaccination (Visit 2, Month 1).

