- To assess the non-inferiority of the responses to MenACWY when given concomitantly with rMenB+OMV NZ to healthy subjects 16-18 years of age compared to MenACWY administered alone as measured by ELISA Geometric Mean Concentrations (GMCs) against each of the serogroups A, C, W and Y, at one month after the (study) vaccination with MenACWY.

Criterion: Non-inferiority will be demonstrated if for each of the four A, C, W and Y strains, the lower limit of the 2-sided 95% CI of the between-group ratio of ELISA GMCs (null hypothesis that the difference in the population means (of the logarithmically [base of 10] transformed hSBA titers) of MenACWY with rMenB+OMV NZ versus MenACWY alone) is $>\text{less than or equal to } \log_{10}(0.5)$ is rejected.

Details regarding the blinding process to the lab personnel performing clinical testing are updated. Following the integration of the two legacy blinding processes with regards to lab personnel, a duly assessment confirmed that the laboratory in charge of the clinical testing can be blinded to the treatment as well as to the subject number. Moreover, in order to prevent the laboratory from linking the consecutive visits to a specific subject, a different subject code will be used for each timepoint tested.

- The 4-fold increase in post-vaccination hSBA titer definition when the pre-vaccination titer is below the LOD, has been modified to: For a pre-vaccination titer $< \text{LOD}$, a post-vaccination titer of \geq fourfold the LOD or $\geq \text{LLOQ}$, whichever is greater.

Section 7.5.1, Recording of concomitant medication/products and concomitant vaccinations, the following criteria was added:

- The use of antipyretic and/or other medications to prevent (prophylactic use) and/or treat fever during the first 7 days after vaccination to be recorded in the eCRF as well.

In **Section 8.2.1 Data collected from subjects**, the following change was made:

- Vaccination history as confirmed by vaccination records, if accessible.
- In Section 8.2.3, Medical history, text on qualified healthcare professional was added as follows:

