where Ab_post represents the log-transformed antibody value of the immunogenicity variable at a given post baseline timepoint, trt indicates the vaccine group, and center the site.

The following SAS code will be used for the ANCOVA model:

```
PROC GLM data = dataset;
  class trt center Ab_pre;
  model Ab_post = trt center Ab_pre;
  lsmeans trt / stderr cl tdiff pdiff;
  estimate 'Group A vs. Group B' trt 1 -1;
run;
```

where Ab_post represents the log-transformed antibody value of the immunogenicity variable at a given post baseline timepoint, trt indicates the vaccine group, center the site, and Ab_pre the log-transformed antibody baseline value of the immunogenicity variable.

If the statistical model does not converge due to the factor “centre”, merging some centres or including instead “country” in the model will be considered.

For each *N. meningitidis* serogroup B test strain (M14459, M07-0241084, 96217 and NZ98/254) and each of the serogroups A, C, W and Y, the percentages of subjects with fourfold increase in hSBA titers, and the corresponding exact two-sided 95% CIs based on the Clopper-Pearson method [[Clopper, 1934](#)] against these strains will be calculated

for each study group at one month after the 1st vaccination and one month after the 2nd vaccination, for serogroup B test strains, and at one month after (study) vaccination of MenACWY, for serogroups A, C, W and Y. The CIs for the rate difference between groups will be constructed using the method of Miettinen and Nurminen [[Miettinen](#), 1985].

The percentage of subjects with fourfold increase in hSBA titers one month after the 1st and one month after the 2nd vaccination, for serogroup B test strains, and one month after (study) vaccination, for serogroups A, C, W and Y, relative to baseline is defined as:

- If the baseline titer is <limit of detection (LOD), then post-vaccination titer should be ≥ 4 x LOD or \geq LLOQ, whichever is greater
- If the baseline titer is \geq LOD but <LLOQ, then post-vaccination titer should be ≥ 4 x LLOQ
- If the baseline titer is \geq LLOQ, then post-vaccination titer should be ≥ 4 x the baseline titer

Summary tables will show unadjusted percentages and unadjusted “between-group” differences.

The following table contains the LOD and LLOQ values to be used.

Table 5 LOD, LLOQ and ULOQ values

Serogroups / B strains	LOD*	LLOQ*	ULOQ*
A	5	12	4295
C	4	8	54828
W	4	8	10057
Y	4	10	7624
M14459	4	5	Not defined
96217	6	14	Not defined

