NZ298/254	4	6	Not defined
M13520	4	6	Not defined

*Strain, assay cut-off(s) and unit(s) might be subject to change during the course of the study (e.g., in case of requalification, revalidation or standardization). In this case, this will be documented either in a protocol amendment or in the clinical report.

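### Protocol Table 6 sets the MenB fourfold-response threshold at four times the LOD for baselines between LOD and LLOQ, where every other current statement of the rule says four times the LLOQ

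*Protocol*

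**What the plan says.** The fourfold increase in hSBA titer is defined in three classes of baseline: below the LOD, from the LOD to below the LLOQ, and at or above the LLOQ. The statements differ only in the middle class.

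- Protocol section 4, Table 6, MenB row: "a post vaccination titer (Visit 2, Month 1 and Visit 4, Month 3) of at least fourfold the LOD".
- Protocol section 1 (synopsis), MenB row: "a post vaccination titer (Visit 2, Month 1 and Visit 4, Month 3) of at least fourfold the LLOQ". SAP section 2 says the same.
- Protocol section 4, Table 6, MenACWY row: "a post vaccination titer (Visit 2, Month 1) of at least fourfold the LLOQ".
- SAP section 5.4.2, for B strains and for A, C, W and Y: "then post-vaccination titer should be ≥ 4 x LLOQ".

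The description of Amendment 1 in Protocol section 12.8 records a change to this definition in the lowest class only: "The 4-fold increase in post-vaccination hSBA titer definition when the pre-vaccination titer is below the LOD, has been modified to" the greater of four times the LOD and the LLOQ.

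SAP section 5.4.2 introduces Table 5 with "The following table contains the LOD and LLOQ values to be used". The table's fourth B-strain row reads "M13520 4 6 Not defined", and there is no row for M07-0241084. SAP sections 5.4, 6 and 6.1 name M07-0241084 as the fourth B strain. The footnote to Table 5 says that strains and cut-offs "might be subject to change during the course of the study", with the record to go in a protocol amendment or the clinical report. SAP section 10.1.3.9 refers the reader to the protocol for the assay cut-off.

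**The concern.** Table 6 is the protocol's formal endpoint table and is current text, not an amendment log. The protocol therefore gives two different rules for the same endpoint, vaccine, visits and baseline class. The Table 6 rule also cannot do what its name says. Any baseline in the class above the LOD itself reaches four times the LOD after less than a fourfold rise. Anyone programming or checking the responder percentages from Table 6 would get different counts from someone using the SAP.

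The strain mismatch is a traceability problem. From the visible SAP, a reader cannot match one of the eight primary immunogenicity hypotheses to a row in the cut-off table.

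**Working it through.** The plan states no figure for this point, so the check is a comparison of the texts followed by direct arithmetic.

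**Inputs.** LOD/LLOQ from SAP Table 5: M14459 4/5, 96217 6/14, NZ98/254 4/6 (printed there as NZ298/254). From Protocol Table 13: M14459 3/5, 96217 6/15, NZ98/254 4/6, M07-0241084 4/4.

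**Formulas for the middle class.**
- Table 6 threshold = 4 × LOD.
- Threshold everywhere else = 4 × LLOQ.
- Limiting rise under Table 6 for a baseline just under the LLOQ = 4 × LOD / LLOQ.

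**Results on SAP Table 5.**

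| Strain | 4 × LOD | 4 × LLOQ | Limiting rise under Table 6 |
|---|---|---|---|
| M14459 | 16 | 20 | 16/5 = 3.2 |
| 96217 | 24 | 56 | 24/14 = 1.71 |
| NZ98/254 | 16 | 24 | 16/6 = 2.67 |

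**Results on Protocol Table 13.** M14459: 12 against 20. 96217: 24 against 60. NZ98/254: 16 against 24. M07-0241084: LOD and LLOQ are both 4, so the class is empty and the rules agree.

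**General check.** In this class the baseline b satisfies LOD ≤ b < LLOQ. Then 4 × LOD / b is at most 4, with equality only at b = LOD, while 4 × LLOQ / b is always above 4. Only the LLOQ rule guarantees a fourfold rise.

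**Size in whole-number titers (SAP Table 5).** If titers are whole numbers, the M14459 class holds only the value 4, and 16/4 = 4.0, so there is no shortfall. The top of the NZ98/254 class is 5, and 16/5 = 3.2. The top of the 96217 class is 13, and 24/13 = 1.85. The conflict is material mainly for 96217, whose class runs from 6 to just under 14.

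**Step at the class boundary.** Under Table 6 a 96217 baseline just under 14 needs 24, and a baseline of 14 needs 4 × 14 = 56. For a 96217 baseline below the LOD the threshold is max(4 × 6, 14) = 24, so Table 6 in effect merges the middle class into the lowest one.

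**Strain and cut-off sources.** Setting SAP Table 5 beside SAP sections 5.4, 6 and 6.1 shows three of the four B strains matched and M07-0241084 unmatched. Setting SAP Table 5 beside Protocol Table 13 shows different values, for example serogroup A 5/12 against 4/5. The pointer in SAP section 10.1.3.9 therefore leads to values other than those Table 5 says will be used.

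**The case against.** **The SAP settles it.** The analysis follows the SAP, which states four times the LLOQ twice, and no analysis text uses the LOD version. The endpoint is reported as percentages with confidence intervals, with no hypothesis attached. The documents do not say how many subjects have a baseline in the affected class, and the 1.7-fold figure is the extreme edge of one class. All of this stands and is why the point is minor. It does not make the Table 6 wording correct.

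**The amendment history is not proof.** The Amendment 1 description says that changes from moving to the sponsor's template are not listed. The silence about this class is therefore weak evidence that the LOD wording was unintended. The stronger evidence is that every other current statement disagrees with it.

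**The strain change is provided for.** Both documents allow the NHBA strain to change before testing and send the record to the clinical report; the Table 5 footnote also allows a protocol amendment. Redacted text may mention M13520, and the plan allows the primary endpoints to be repeated on another panel of strains. A reader might infer an undocumented switch of a co-primary strain, or that M07-0241084 has no cut-offs at all. The documents support neither: the route for recording a change is stated, and Protocol Table 13 gives M07-0241084 an LOD and LLOQ of 4. That M13520 is the NHBA replacement is itself an inference from its place in the table.

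What remains is that SAP section 8 logs the ELISA-to-ECL change although the clinical report will record it too, and says nothing about the strain. The SAP Amendment 3 log gives only alignment with current cut-off values as the reason for updating Table 5.

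**Conclusion.** The contradiction in Protocol Table 6 is real, and the Table 6 version is the wrong one for an endpoint called a fourfold increase. The severity is minor. It affects the middle baseline class of a descriptive secondary responder percentage for three B strains, most of all 96217 (24 against 56). The sizes assume the SAP Table 5 cut-offs and a literal reading of Table 6. The number of subjects affected is unknown.

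Three stronger readings should be set aside.
- The non-inferiority conclusions are not at risk. The co-primary criteria rest on GMT ratios, and the sample size on their SDs and margin, none of which uses the fourfold rule.
- The 4/4 cut-offs of M07-0241084 and the 4/6 cut-offs of M13520 should not be compared as if applied to the same titers. They belong to different strains, and only one set would be relevant to a given result.
- Half-cut-off substitution is not shown to move subjects between baseline classes. That would require reading the cut-off as the LLOQ and classing on substituted values. SAP section 10.1.3.9 limits substitution to GMT and GMC calculation, and a rule that separates below-LOD from LOD-to-LLOQ presupposes unsubstituted titers.

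**What to change.** 1. In the MenB row of Protocol Table 6, change LOD to LLOQ in the middle-class threshold, at the next amendment or by whatever change route the sponsor's rules allow. Protocol section 12.4.1.2 describes an administrative change as a minor correction or clarification, but the glossary restricts it to logistical or administrative aspects, so the route is for the sponsor to decide.
2. State in SAP section 8 which NHBA strain is tested, as is done there for the ELISA-to-ECL change, and make Table 5 and the strains named in SAP sections 5.4, 6 and 6.1 agree. SAP section 2 can stay aligned with the protocol, as section 8 already arranges for the ELISA change.
3. Point SAP section 10.1.3.9 to SAP Table 5, rather than the protocol, for hSBA cut-offs.

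The cost is one word in the protocol, with whatever approval the chosen route needs, and a few lines in the SAP. No new data are needed, and the co-primary tests and sample size do not change.
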